- a. Left atrial remodeling will be measured by LA volume index, diastolic function grade, and estimate of LA pressure via echocardiography at baseline and one year follow-up.
- b. Cardiovascular risk factors will be compared at baseline, six months and one year. These include: Systolic Blood Pressure, Hemoglobin A1C (marker of average blood sugar over 3 months), body mass index, waist circumference, and low density lipoprotein (LDL cholesterol), apnea hypopnea index (AHI), and fitness classification (metabolic equivalents (METS) achieved on exercise stress test).
- c. Using pharmanet data, total cost of all medications and specific cost for antiarrhythmic agents, antihypertensive agents, diabetes and cholesterol lowering medications will be recorded and compared at baseline and one year. Hospital Emergency visits will also be compared.

5. Methodology

5.1 Proposed Study Design: This is a parallel-group randomized controlled trial. Consecutive patients meeting eligibility criteria that are seen for routine cardiology follow-up, or those referred by family physicians, will be invited to participate in this study. Patients who accept the possibility of a year-long diet counseling and exercise program will be randomized and stratified to ‘control arm’ *versus* ‘intervention arm.’ Forty patients will be randomized to control arm and 40 patients randomized to the intervention arm. Intervention will include Phase 1, a six month program including three months of diet counseling combined with home exercise, followed by three months (starting at week 13) of an in-hospital, Cardiac rehabilitation exercise program. Phase 1 also includes risk factor management by an internist who specializes in cardiovascular risk factors. Phase 2 of the intervention will include six months of home-based maintenance exercise and diet (starting at week 25). Assuming approximately 40% of eligible patients agree to participate (based on our experience that there is a high willingness to participate in both research studies and the cardiac rehabilitation program), and given that we were able to recruit 200 research participants in one year for a previous study (35), we estimate that it is feasible to recruit a total of 80 participants over a three to six month period.

5.2 Participants: Patients will provide written, informed consent. All study procedures will be reviewed and approved by the UBC Clinical Ethics board and the VCH operational approval process.

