5.4 Data Analysis (and sample size)

This is a parallel, randomized control study. The researcher analyzing results will be blinded to the patient's group. A statistician will be hired to analyze data and a statistician from C2E2 (UBC) has reviewed the study design. Normally distributed data will be analyzed using repeated measures analysis of variance (ANOVA) to calculate changes over time (baseline, six-months, one-year) within each group. Between groups analyses on differences from baseline will be analyzed using independent *t*-tests. Statistical significance will be set *a priori* as *p*<.05. Continuous variables will be described by group using mean (SD) (or median (P25, P75) if the data are skewed); and categorical variables will be described by frequency (percent).

To calculate effect size for the intervention group, we considered the moderate effect sizes reported in exercise studies measuring cardiorespiratory changes (e.g., Huang et al. (2016) (40) reported a moderately high effect size of 0.64 for aerobic changes following an exercise program in older adults). Using G-power software (*alpha* = .05), the

sample size required to achieve 80% power to detect an effect is 22 per group (two-tailed, or repeated measures design) (44). Based on the data from Malmo and colleagues (26) reporting a large effect size (1.0) for the difference in time spent in AF pre- and post-exercise, a sample size of less than 10 participants would achieve a power of 80%. The AF studies to-date report low attrition rates. For example, Pathak et al. (19) reported 10% attrition in the risk factor intervention group, and Malmo et al.(26) reported a 0% attrition in the three-month interval-training program. Given that the Richmond Cardiac Rehabilitation program similarly reports low drop-out rates (of approximately 2%), we have allowed for greater than 10% attrition. Including 40 participants in the intervention arm, and 40 participants in the control arm will allow for more than 10% drop out while still maintaining adequate power to detect an effect.

6. Summary and Impacts on Practice

Richmond has experience in recruiting patients with AF, cardiac rehabilitation, and bariatric diet therapy program. Our Richmond team of specialists, combined with strong partnerships with our colleagues at VGH that have experience with research trials will help guide us in implementing a successful research project.

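### Dropout is met only with spare numbers: the between-group change-score t-test leaves out anyone who misses the visit, so the one-year comparison can be biased if loss differs by arm and relates to outcome

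*Combined protocol and SAP*

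**What the plan says.** Section 5.4 Data Analysis (and sample size) is the only place where attrition meets the analysis. After citing low dropout elsewhere (10%, 0% and about 2%), it concludes that 40 per arm "will allow for more than 10% drop out while still maintaining adequate power to detect an effect".

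The comparison of arms is stated in one sentence: "Between groups analyses on differences from baseline will be analyzed using independent" *t*-tests. Repeated-measures ANOVA is also planned, but only for change over time within each group.

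The documents name no missing-data method, analysis population, imputation or sensitivity analysis. Section 5.4 Data Collection schedules most measurements at baseline, six months and one year in both groups. Echocardiography is done at baseline and one year only.

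**The concern.** A t-test on change to one year can include only people seen at one year. Spare numbers restore precision but do not make those who return representative of those randomised.

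The arms give different reasons to leave. Under section 5.1, "Patients who accept the possibility of a year-long diet counseling and exercise program will be randomized". Those allocated to control then receive usual care, a step tracker and a handout. The program arm is offered about 39 hospital sessions in 24 weeks: 1 + 12 + 1 dietary and 1 + 24 exercise sessions, if classes are weekly. The phone check-ins and walking group in Phase 2 are described only for the program arm, and they target adherence rather than outcome assessment.

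The attrition figures offered as reassurance all come from intervention groups or rehabilitation programs. The 2% figure comes from an 8-week program and the 0% from a three-month one. Section 5.4 cites no control-arm rate.

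At stake is the one-year comparison, which carries the claim that benefit lasts beyond the supervised phase.

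**Working it through.** **The plan's own figure.** The plan says the "sample size required to achieve 80% power to detect an effect is 22 per group (two-tailed, or repeated measures design") for a standardised effect of 0.64. A paired two-sided t-test (noncentral t, alpha 0.05, power 80%) needs 21.2, so 22, which reproduces the figure. The planned two-sample test at 0.64 needs 39.3, so 40 per arm with nobody lost. Its power is 80.7% at 40 and 76.4% at 36 (10% loss). So at this effect size the margin is not there for the between-group test. That is a separate power matter, and the bias question below would remain with any number of participants.

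**How loss turns into bias.** Let a fraction f of the program arm be lost, and let those lost have a one-year change g SD worse than the whole arm. Let control loss be random. Then

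bias of the change-score difference = f/(1 − f) × g.

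**Simulation A (assumed mechanism).** Three normally distributed visits with correlation 0.5–0.7. Program-arm dropout odds rise 2.1–4.5-fold per SD worse observed six-month change, and control dropout is random. The comparator is the likelihood estimate: within each arm, regress the one-year value on the baseline and six-month values among those seen, average the prediction over everyone randomised, and subtract mean baseline. With dropout only after six months, this is equivalent to an unstructured mixed model.

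| Dropout, program vs control | t-test bias (SD of change) | Likelihood bias | Implied g |
|---|---|---|---|
| 10% vs 2% | 0.04–0.06 | near 0 | bias ÷ 0.111 = 0.36–0.54 |
| 20% vs any random rate | 0.06–0.12 | near 0 | bias ÷ 0.25 = 0.24–0.48 |

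Against the planning effect, 0.04/0.64 to 0.06/0.64 is 6–9%, and 0.06/0.64 to 0.12/0.64 is 9–19%.

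**Effect on false positives.** At 10% versus 2%, SE = √(1/36 + 1/39.2) = 0.231. The chance of a favourable false positive is P(Z > 1.96 − bias/SE). A bias of 0.04 gives P(Z > 1.79) = 3.7%, and 0.06 gives P(Z > 1.70) = 4.5%, against a nominal 2.5%. The likelihood estimate has essentially the same SE.

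**Simulation B (what the remedy cannot do).** Here both arms lose people by the same, steeper mechanism (log-odds slope 2 per outcome SD) at unequal rates. Bias is in SD of change at visit correlation 0.5.

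| Dropout, program vs control | Dropout follows | t-test | Likelihood |
|---|---|---|---|
| 10% vs 2% | observed six-month change | 0.056 | 0.001 |
| 20% vs 5% | observed six-month change | 0.087 | −0.005 |
| 10% vs 2% | unseen one-year change | 0.109 | 0.078 |
| 20% vs 5% | unseen one-year change | 0.182 | 0.135 |
| 20% vs 20% | either | about 0 | about 0 |

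When dropout follows the unseen outcome, the likelihood estimate keeps 0.078/0.109 = 72% and 0.135/0.182 = 74% of the bias. With the milder odds of simulation A it is again roughly 70–75%.

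**The case against.** - **Attrition may be too low to matter.** The plan cites 0–10%. With 2% program-arm loss and the odds assumed above, the bias is at most 0.02 SD. This stands as a limit on size. But the plan itself allows for more than 10%, and its figures do not cover a year-long trial with a control arm.
- **The direction is not known.** A reader might infer that the t-test inflates the benefit. The documents do not support that, because it depends on loss being related to outcome mainly in the program arm. With the same mechanism in both arms and 15% control versus 10% program loss, the bias reverses to −0.02 to −0.03 SD. This stands.
- **A mixed model may not help where loss is likeliest.** The session burden ends at week 24, so it would mostly cause loss before the six-month visit. With 20% program-arm loss that follows a six-month change never recorded, the t-test bias is 0.09–0.10 SD, and a likelihood estimate with only baseline keeps 0.05–0.07 SD. A reader should therefore not infer that the model protects the comparison outright.
- **The ANOVA.** Listwise deletion from the ANOVA is tempting to add. The ANOVA is within-group, so it is not the comparison of arms at risk.
- **Assessment already covers everyone.** Section 5.3 repeats exercise tests in all participants, and section 5.4 Data Collection covers both groups. Neither makes assessment conditional on staying in the program. Explicit wording is still worth having.
- **The simulations are Gaussian.** They give no magnitude for percent time in AF or CCS-SAF. This stands.

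**Conclusion.** The point holds as a conditional one. As written, the one-year comparison leaves out anyone without that visit, and nothing in the plan addresses the bias that can follow. For near-normal outcomes the plausible size at the plan's own attrition figures is modest, about 0.04–0.06 SD at 10% versus 2%. It rises to 0.06–0.12 SD at 20% program-arm loss, which is above the rates that the plan cites. These figures rest on assumed normal outcomes, visit correlations and dropout odds; none of the last two is given in the documents.

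A likelihood-based model is the better default. It uses six-month data already planned, loses essentially no precision, and removes the bias when dropout depends on what was observed. It does not remove bias from dropout that depends on unseen outcomes, so it needs a sensitivity analysis and continued follow-up beside it. The change is worth making before analysis, but the omission does not by itself invalidate the trial.

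**What to change.** 1. For near-normal outcomes measured at all three visits, replace the between-group change-score t-test with a likelihood-based mixed model: all randomised participants with any data, arm-by-visit terms, unstructured covariance.
2. For percent time in AF and CCS-SAF, multiply impute within arm from baseline and six-month values before the chosen non-normal analysis. First confirm that CCS-SAF is collected at six months: section 5.4 Data Collection lists it under medical history, which is exempted from the repeat schedule, while hypothesis ii expects AF symptoms at six months.
3. Add one sensitivity analysis that shifts imputed program-arm values toward no benefit.
4. State that people who stop the program are still invited to the six-month and one-year assessments already planned for both groups.

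The cost is SAP wording, a little more analysis work, and reliance on a missing-at-random assumption. There is little gain for echocardiography, which has no six-month visit, or for people with no post-baseline data. For them, step 4 matters most.
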